10.3.10 Serious Adverse Events

All SAEs, as defined in Section [11.3.1](#), will be evaluated from the time the consent is signed through 90 days following cessation of trial treatment or EOS (whichever is later), or 28 days following cessation of trial treatment if the patient initiates new anti-cancer therapy. Any SAE must be reported to Dynavax or its designee within 24 hours of the knowledge of the event.

An SAE, whether assessed as related or not related to study treatment, will be followed until considered stable, resolved, or until EOS, or the patient initiates new anti-cancer therapy (whichever is earlier).

10.3.11 Concomitant Medications

Any prescription medication, over-the-counter drug or natural/herbal preparations, including vitamins and dietary supplements, and transfusions, including those for the treatment of any AEs, taken by the patient from Screening through 28 days after permanent discontinuation of all study treatment must be recorded in EDC.

10.4 Disease Assessments

NOTE: As of Amendment 9, all disease response assessments, including the timing and type of imaging, are to be performed per the Investigator based on local standard of care; the data will not be collected and no longer need to be recorded in the CRF. This section has been updated accordingly.

Disease assessment will consist of: 1) clinical assessment of superficial lesions, and 2) radiographic imaging (See Section 8.2.1.2). Such assessments will be performed at baseline no more than 28 days prior to the first dose of trial treatment and at the discretion of the investigator as per local standard of care thereafter ([Appendix 1](#) through [Appendix 4](#)).

10.4.1 Confirmation of Progressive Disease (Based on irRECIST)

NOTE: As of Amendment 9, irRECIST is no longer applicable and this section has been deleted accordingly. All imaging will be performed as per local standard of care guidelines. It is at the discretion of the investigator whether to repeat imaging for confirmation and whether to continue a patient on study treatment.

Determination of PD is per local standard of care and local assessment guidelines.

10.5 Pharmacodynamic Assessments

NOTE: As of Amendment 9, this section is no longer applicable.

- Phase 1: Blood will be collected for assessing IFN-inducible gene expression. Collections are to be done pre-injection on treatment Days 1 and 8 ([Appendix 1](#)). On Day 9, the sample is to be collected 24 hours after the Day 8 injection.
- Phase 2: Blood will be collected for possible future testing of RNA gene expression. Collections are to be done at Screening and pre-injection on study days as specified in [Appendix 2](#) and [Appendix 4](#).

For both phases of the study, an extra aliquot of serum will be collected and stored frozen for possible future testing at time points outlined in [Appendix 1](#) through [Appendix 4](#).

10.6 Immunogenicity Assessments

NOTE: As of Amendment 9, this section is no longer applicable.

To determine if antibodies to SD-101 are generated following administration of SD-101, blood will be collected as outlined in [Appendix 1](#) through [Appendix 4](#).

10.7 Exploratory Assessments

NOTE: As of Amendment 9, Sections 10.7.1, 10.7.2, and 10.7.3 are no longer applicable.

10.7.1 Expression Profiling

Exploratory assessments for PD-L1 expression by immunohistochemistry, and RNA expression profiling to determine the infiltration of lymphocytes and other immune-related responses may be assessed and correlated with clinical response.

10.7.2 Neoantigen and DNA Mutational Analyses

Studies of genetic mutations, polymorphisms, and rearrangements are increasingly important in understanding and ultimately predicting responses to cancer therapies targeting the anti-tumor immune response. For recurrent or metastatic HNSCC, sequence analysis of selected samples of tumor and blood may be conducted as an exploratory assessment.

In addition to understanding the anti-tumor responses, the sequence analysis can identify mutations that, when expressed by a tumor, are potentially immunogenic (ie, neoantigens) and can inform additional targeting therapeutic strategies for future clinical studies. Confirmation of the identification of neoantigens will be done using PBMCs, which will be stimulated with peptides corresponding to the identified neoantigens and analyzed for activation through secretion of cytokines by ELISpot. Sequencing may be conducted for biopsies collected in the HNSCC trial. PBMCs for confirmation of the identification of neoantigens may be obtained at sites that are able to isolate and freeze viable PBMCs at the time of biopsy collection in the HNSCC portion of the trial. Collection time points are indicated in the Schedule of Trial Events located in [Appendix 2](#) and [Appendix 4](#). The Laboratory Manual will provide details on the procedure for sample collection.

10.7.3 Human Papillomavirus Status

For HNSCC patients only, HPV status (positive + or negative) at Screening will be determined from either archival test results or new testing as described in the Schedule of Trial events [Appendix 2](#) through [Appendix 4](#).

10.8 End-of-Study/Safety Follow-up Visit

NOTE: As of Amendment 9, trial procedures have been simplified. This section has been updated accordingly.

The EOS /Safety Follow-up Visit is required after permanent discontinuation of trial treatments (both SD-101 and pembrolizumab), regardless of the reason for discontinuation [to be completed 28 (\pm 3) days after last dose of trial treatment].

10.9 Unscheduled Visit for Safety or Disease Progression

NOTE: As of Amendment 9, all disease assessments will be performed as per local standard of care guidelines. Confirmation of disease progression by repeat imaging is not mandatory.

A UNS should be performed if there is suspected disease progression or patient safety concerns. Procedures for the visit are at the discretion of the investigator according to local standard of care guidelines.

If the patient has permanent discontinuation of trial treatments (both SD-101 and pembrolizumab), an EOS Visit (Section 10.8) should be scheduled 28 days after the date of last trial treatment administration.

10.10 Duration of Follow-up

NOTE: As of Amendment 9, follow-up procedures have been simplified. This section has been updated accordingly.

All patients must be followed for at least 28 days after their last dose of trial treatment (Section 11.0). Patients who discontinue trial treatment without documented disease progression should be assessed per local standard of care guidelines until the EOS/Study Follow-up visit is complete.

11.0 INVESTIGATOR'S RESPONSIBILITIES

This trial will be conducted in accordance with the protocol, the International Council for Harmonisation (ICH) E6(R2) GCP guidelines and applicable US Code of Federal Regulations (CFR) and local regulatory requirements. Investigators are responsible for monitoring the safety of patients throughout the course of the trial and for providing appropriate medical care. The investigator will perform all tasks directly or is responsible for overseeing and training qualified site personnel as delegated to perform trial tasks. In addition, investigators are responsible for alerting Dynavax to any event that seems unusual and for reporting all AEs, event of clinical interests (ECIs), SAEs, pregnancies, and deaths in the appropriate CRFs.

11.1 Injection-site Reactions

Local injection-site reactions will be assessed and documented per Section 10.3.8. Local injection-site reactions are considered AEs if they persist longer than 7 days and need to be recorded and reported per protocol Section 11.2. The severity of the injection-site reactions will be graded using the Toxicity Grading Scale for Healthy Adult and Adolescent Volunteers Enrolled in Preventive Vaccine Clinical Trials ([Appendix 5](#)).

The severity of all injection-site reactions that are not listed on the Toxicity Grading Scale for Healthy Adult and Adolescent Volunteers Enrolled in Preventive Vaccine Clinical Trials ([Appendix 5](#)) will be assessed and confirmed by the investigator and will be graded using the adapted NCI CTCAE Version 4.03 grading scale ([Table 11-1](#)).

Further information is provided in the Study Reference Manual.

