4.3.2.2 Secondary Endpoints

- Incidence of injection-site reactions, AEs, and SAEs

The following Secondary Endpoints (Phase 2) will not be collected as of Amendment 9:

- Time to response using RECIST v1.1
- Duration of response per RECIST v1.1
- Radiographic PFS per RECIST v1.1

4.3.2.3 Exploratory Endpoints – No longer collected as of Amendment 9

- Radiographic primary and secondary endpoints evaluated using irRECIST ([Appendix 6](#), Immune-related RECIST)
- Changes in correlative biomarkers including tumor-infiltrating lymphocytes and PD-L1 expression at baseline and after SD-101 treatment
- Changes in potential tumor neoantigens in patients with recurrent or metastatic HNSCC
- Changes in the expression of IFN-inducible genes in whole blood in patients with metastatic head and neck squamous cell carcinoma

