7.6 Dose Modification, Dose Delays, and Missed Doses

NOTE: As of Amendment 9, irRECIST for the determination of disease progression is no longer applicable and this section has been revised accordingly.

Only a limited number of patients have been treated with SD-101, and to date, the most common toxicities include transient Grade 1 to 2 flu-like symptoms. In mice, SD-101 has been injected intratumorally concurrently with a neutralizing anti-mouse PD-1 antibody. In multiple experiments using high doses of SD-101 (approximately 2 mg/kg), no evidence of acute morbidity or mortality in mice was observed that could be due to the interaction of the 2 agents.

To protect patient safety, patients will be closely monitored for any additional or synergistic toxicities observed with the combination.

Withhold SD-101 for any Grade ≥ 3 injection-site reaction or drug-related AE that is not a DLT (see Section 9.1). SD-101 treatment may be resumed once the AE has resolved to Grade 0 or 1 with standard treatment. SD-101 must also be held for an ANC count of < 1500 cells/mcL.

Patients will be treated at the dose in their assigned Cohort and individual dose adjustment (reduction or increase) of SD-101 or pembrolizumab will not be permitted.

Delayed dosing of SD-101 would be preferred over completely skipping a dose as long as the interval between SD-101 dosing is not less than 5 days with subsequent return of SD-101 dosing to per protocol schedule of events. If the 5-day interval cannot be adhered to, then the injection must be skipped to allow a minimum of 5-day interval window between the off-scheduled injection and next injection on schedule. After a delayed or skipped dose, dosing will return to the original interval as described under Schedule of Trial Events.

For Phase 1, if ≥ 2 doses are missed during the DLT assessment period for any reason or if ≥ 4 doses are missed due to AEs following the DLT period, then SD-101 should be permanently discontinued. For Phase 2, if ≥ 4 doses are missed due to AEs, then SD-101 should be permanently discontinued.

If SD-101 dosing is delayed for more than 3 days, then the hematology and chemistry laboratory collections listed in the Schedule of Trial Events ([Appendix 1](#) through [Appendix 4](#)) or the planned day of dosing that were missed should be done prior to dosing on that day (eg, if Day 22 dosing is delayed and SD-101 is dosed on Day 26, then all the Day 22 labs should be repeated pre-dose on Day 26).

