10.3.8 Injection-site Reaction Assessments

Assessments of injection-site reactions will be collected for a minimum of 90 minutes following each of the first 4 initial weekly SD-101 injections in Phase 1 as outlined in the Schedule of Trial Events ([Appendix 1](#) through [Appendix 4](#)) at the clinical site and as reported by the patient on the Diary Card for 7 days in Phase 1.

With Protocol Amendment 6, Diary Cards are discontinued in Phase 2; however, injection site reactions listed on the Toxicity Grading scale for Healthy Adult and Adolescent Volunteers Enrolled in Preventive Vaccine Clinical trials ([Appendix 5](#)) that persist for more than 7 days will be recorded as AEs (Section 11.1).

Prior to the first 4 initial weekly injections of SD-101 in Phase 1 ([Appendix 1](#)), patients will receive a new Diary Card with instructions to measure and record local injection-site reactions and solicited AEs that occur post SD-101 injection. The completed Diary Cards will be reviewed with the patients at their next study visit.

For the first 4 weekly injections of SD-101 in the first course in Phase 1, Dynavax will capture all injection-site reactions that occur, even if the diameter of the largest dimension does not meet a Grade 1 on the severity scale ([Appendix 5](#)). As such, any reaction smaller than this size cannot be graded, but will still be recorded in the clinical database and the severity will be marked as *not applicable (N/A)*.

All data documented by the patient on Diary Cards will be collected, reviewed by the trial nurse/coordinator with the patient, and recorded on the appropriate CRF.

Injection-site reactions need to be recorded also on the AE eCRF for the following:

- 1) The duration of the injection-site reaction exceeds 7 days
- 2) The verbatim term for the injection-site reaction is different than the terms listed for the diary and provided for recording on the injection-site reaction eCRF
- 3) The injection-site reaction qualifies as an SAE.

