11.3.2 Serious Adverse Event Reporting Requirements

Any SAE that occurs from the time the consent is signed through 90 days following cessation of trial treatment or EOS (whichever is later), or 28 days following cessation of trial treatment if the patient initiates new anti-cancer therapy, whether or not the SAE is related to the trial treatment (SD-101 and/or pembrolizumab), **must be reported to Dynavax or its designee within 24 hours of investigator awareness of the event.** The contact information for reporting SAEs is provided in the Study Reference Manual. General SAE reporting instructions are as follows:

- Submit SAE documents according to instructions in the Study Reference Manual.
- Record all SAEs on the AE CRF.
- For SAEs, record the primary event on the AE CRF; describe events occurring secondary to that primary event on the SAE form in the narrative description of the case.
- Death is an outcome, not an event. Record the event that resulted in the death as the fatal event on the AE CRF.
- For hospitalizations for surgical or diagnostic procedures, record the illness leading to the surgical or diagnostic procedure as the SAE, not the procedure itself. Capture the procedure in the narrative as part of the action taken in response to the illness.
- Elective hospitalizations will not be considered SAEs and do not need to be reported. Complications that prolong elective hospitalizations should be recorded as SAEs. Emergency room visits of less than 24 hours do not meet the criterion of hospitalization for SAE reporting purposes.

The SAE report should contain, at a minimum, the following information:

- Patient identifiers (ie, patient number)
- Suspected medicinal product
- AE term (must be listed as serious)
- Contact information for person reporting event

The relationship of the SAE to trial treatment will be assessed by the investigator (Section 11.4.2). Follow-up information should be actively sought and submitted as it becomes available.

The investigator will assess relationship to trial treatment. In addition, the sponsor will assess relationship to trial treatment and determine expectedness to SD-101 based on the current SD-101 Investigator's Brochure and to pembrolizumab based on the pembrolizumab Investigator's Brochure. The sponsor will report all SD-101 suspected and unexpected serious

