Local Reaction to Injectable Product	Mild (Grade 1)	Moderate (Grade 2)	Severe (Grade 3)	Potentially Life Threatening (Grade 4)
Pain	Does not interfere with activity	Repeated use of non-narcotic pain reliever > 24 hours or interferes with activity	Any use of narcotic pain reliever or prevents daily activity	Emergency room (ER) visit or hospitalization
Tenderness	Mild discomfort to touch	Discomfort with movement	Significant discomfort at rest	ER visit or hospitalization
Erythema/Redness ^a	2.5 – 5 cm	5.1 – 10 cm	> 10 cm	Necrosis or exfoliative dermatitis
Induration/Swelling ^b	2.5 – 5 cm and does not interfere with activity	5.1 – 10 cm or interferes with activity	> 10 cm or prevents daily activity	Necrosis

Source: ([Center for Biologics Evaluation and Research 2007](#)).

^a In addition to grading the measured local reaction at the greatest single diameter, the measurement should be recorded as a continuous variable.

^b Induration/swelling should be evaluated and graded using the functional scale as well as the actual measurement.

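### Severity grade does not trigger AE recording of injection-site reactions, so short, non-serious Grade 3–4 reactions can go unrecorded, mainly in Phase 2 after Amendment 6

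*Protocol*

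**What the plan says.** Protocol Section 11.1 sets the AE rule by duration: "Local injection-site reactions are considered AEs if they persist longer than 7 days and need to be recorded". It refers to Section 10.3.8 for assessment and documentation.

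Section 10.3.8 is wider: "Injection-site reactions need to be recorded also on the AE eCRF for the following", followed by three separate triggers:

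- "The duration of the injection-site reaction exceeds 7 days";
- "The verbatim term for the injection-site reaction is different than the terms listed for the diary" and for the injection-site reaction eCRF;
- the reaction qualifies as an SAE.

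Footnotes k (for Phase 2) and bb (Phase 1 diary) to Appendices 1–4 name duration alone. Section 10.3.8 also states that Phase 2 diary cards stopped with Amendment 6.

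Appendix 5 gives Grade 4 pain as "Emergency room (ER) visit or hospitalization", with an equivalent entry for tenderness. Section 11.3.2 adds: "Emergency room visits of less than 24 hours do not meet the criterion of hospitalization for SAE reporting purposes". Section 11.3.1 keeps the important-medical-event criterion, which is a matter of judgment.

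The Phase 2 secondary endpoint in Section 4.3.2.2 that survives Amendment 9 is "Incidence of injection-site reactions, AEs, and SAEs". SAP 9.7.2 tabulates injection-site reactions by maximum severity, injection and analysis group, and names the diary card as the source.

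**The concern.** Local reactions are among the most common toxicities that Section 2.6 reports for SD-101, and their incidence belongs to the only Phase 2 endpoint still collected. One would expect any severe reaction to reach either the AE tables or a dedicated reaction table. As written, a severe but short and non-serious reaction need not reach the AE tables. For Phase 2 patients without diaries, the dedicated table has no stated source either. The reported severe local toxicity would then be too low, and too low by different amounts in the groups that the SAP sets side by side.

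**Working it through.** No power or sample-size figure is involved. The check is a trace through the rules, followed by a count of scheduled assessments.

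**Step 1. Trace of a reaction lasting 7 days or less** (Sections 10.3.8, 11.1, 11.3.1, 11.3.2; Appendix 5)

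- (a) Grade 3, listed term, not serious: no AE record required, no SAE record.
- (b) Grade 4 pain or tenderness through an emergency-room visit under 24 hours, not judged an important medical event or otherwise serious: no AE record required, no SAE record.
- (c) The same visit judged medically important or life-threatening: SAE, so on the AE eCRF.
- (d) Inpatient hospitalization: SAE, so on the AE eCRF.
- (e) Any term not on the list: on the AE eCRF.

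The gap is (a) and (b).

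**Step 2. Other places where (a) and (b) could appear**

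- Phase 1: the diary covers 7 days after each of the first 4 injections, and Appendix 1 marks an injection-site assessment at all 4 + 7 = 11 injections. These cases should be visible there.
- Phase 2, Cohorts 5–8 (Appendix 4): injections on Days 1, 8, 15 and 22, then every 21 days from Day 43 to Day 358. (358 − 43)/21 + 1 = 16, so 4 + 16 = 20 injections. The assessment row is marked at 4 of them, so 16/20 = 80% have none.
- Phase 2, Cohorts 1–4 (Appendices 2 and 3): 2 × (4 + 7) = 22 injections, row marked at 4, so 18/22 = 82% have none. These cohorts opened and enrolled before Amendment 6, while diaries were in use, so this count overstates their gap.

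**Step 3. Patients affected**

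Cohorts 5, 6 and 7 were added at Amendment 6 and Cohort 8 at Amendment 7. Planned numbers: 25 + 25 + 25 + 50 = 125. Planned Phase 2 total: 160 + 100 = 260. 125/260 = 48%.

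**Step 4. Effect on the analysis groups (SAP 2.0)**

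The melanoma 2 mg groups pool Phase 1 patients, who had diaries, with Cohort 5 or Cohort 8, who did not. In HNSCC, Cohorts 6 and 7 are in the 2 mg groups. The 8 mg groups come from Phase 1 and from Cohorts 1–4, which opened with diaries. A 2 mg versus 8 mg contrast in injection-site reactions is therefore mixed with a difference in how the reactions were collected.

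**The case against.** The best defence is that short local reactions are kept out of the AE tables on purpose and reported in their own table, by severity, under SAP 9.7.2. That works for Phase 1. It does not work for Phase 2 patients without diaries, because the diary is the only source that table names.

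Second, the emergency-room case is not automatically lost. Section 11.3.2 removes only the hospitalization criterion, and one of the examples of an important medical event in Section 11.3.1 is treated in an emergency room. This stands as far as it goes: the route exists but depends on judgment, so case (b) is possible rather than certain.

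Third, there is other capture. Patients are observed for 90 and later 30 minutes after injections (footnote cc), and AEs are reviewed at those visits. The site must be back to Grade 0 or 1 before re-injection (Section 9.3.1). Supportive therapies, concomitant medications and reasons for interruption are documented (Sections 9.3.1, 10.3.11, 7.6). This also stands, and a reader who infers that no trace exists would be wrong. But none of these requires a graded record of a short reaction.

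Fourth, a reader might infer from "Withhold SD-101 for any Grade ≥ 3 injection-site reaction" in Section 7.6 that many dose holds go uncounted because the reaction behind them is not an AE. The schedule does not support this. Of the 19 gaps between 20 injections in Cohorts 5–8, 3 are weekly and 16 are 21 days. A reaction gone within 7 days will rarely meet the next injection in the weekly part, and will not in the 3-weekly part.

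Finally, the Study Reference Manual and the injection-site reaction eCRF are not among the documents and may add detail. Enrollment is closed, so a protocol change reaches only the remaining doses.

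**Conclusion.** The point holds in this form: grade is not an AE-recording trigger, and a listed, non-serious Grade 3 or 4 reaction of 7 days or less need not appear in AE or SAE data. It matters chiefly in Phase 2 after Amendment 6, above all in Cohorts 5–8 (about 48% of planned Phase 2 patients, with 80% of injections lacking a scheduled injection-site assessment).

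Two stronger readings should be resisted. Section 11.1 and footnotes k and bb, read alone, suggest that duration is the only route to AE status. Section 10.3.8 shows that unlisted terms and SAEs are recorded whatever their duration, so the AE tables are not confined to prolonged reactions. It is also tempting to scale down the 13.6% Grade 3 or higher injection-site pain in Section 2.6. That figure is already reported as treatment-related AEs from this trial. It may have passed through the 7-day rule, in which case scaling it would filter twice. The direction of the bias is clear, but its size cannot be estimated.

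The conclusion assumes that sites follow the protocol text and that no unseen manual imposes a grade trigger.

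**What to change.** - **Protocol 10.3.8, 11.1 and footnote k:** add that any injection-site reaction of Grade 3 or higher on Appendix 5 is recorded on the AE eCRF regardless of duration. Bring 11.1 and footnotes k and bb into line with the full trigger list in 10.3.8.
- **SAP 9.7.2:** name the AE or eCRF source for Phase 2 patients without diaries. State that short reactions before the change were not systematically captured, so injection-site rates are not comparable between diary and non-diary patients.
- **Data already collected:** where reasons for interruption, supportive therapies or concomitant narcotics point to an unrecorded Grade 3 or higher reaction (narcotic use for pain is Grade 3 on Appendix 5), query it. List what is found separately and do not merge it into the SAP 9.7.3 tables, because recovery will be selective.

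Cost: wording changes, a small query round before database lock, and a slightly higher reported Grade 3 or higher rate. The change concerns recording only and alters no dosing rule.
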